9.3. LEVEL OF SIGNIFICANCE

The primary assessment of the dose-response will be evaluated using a 5% level of significance. Since both co-primary endpoints will be required to be significant at the 0.05 level, there is no adjustment needed for multiple comparisons.

All other reported *p*-values will be considered descriptive and hypothesis generating.

9.4. PROCEDURE FOR ACCOUNTING FOR MISSING, UNUSED, OR SPURIOUS DATA

Any missing, unused, or spurious data will be noted in the final clinical study report. Multiple imputations will be employed to analyze incomplete data sets under the assumption that missing data are, at worst, characterized as missing at random (MAR). The reasons for missing data will be recorded and the impact of these reasons and any treatment group imbalance on the assumption of MAR will be evaluated. Imputation will be carried out only on the co-primary endpoints and time points.

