Following randomization, subjects will return to the clinic for evaluation at Study Visit 3 (Day 8 ± 1 day), Visit 4 (Day 15 ± 1 day), Visit 5 (Day 22 ± 1 day) and Visit 6 (Day 29 ± 1 day). At Visits 3 (Day 8 ± 1 day) and 5 (Day 22 ± 1 day) evaluations will include [REDACTED] and subject-rated assessment of ocular discomfort. A complete study evaluation will be conducted at Study Visits 4 and 6. Subjects will be released from the study at the end of Visit 6 (Day 29 ± 1 day).

Assessments will include

- Investigator-rated assessment of posterior lid margin hyperemia
- [REDACTED]
- Investigator-rated assessment of conjunctival hyperemia
- Investigator-rated assessment of the character of the meibomian glands' contents
- Investigator-rated assessment of the expressibility of the meibomian glands
- Tear film break up time (TFBUT)
- Corneal fluorescein staining

	
• [REDACTED] discomfort assessment• In-clinic subject-rated assessment of ocular discomfort• Best corrected visual acuity (BCVA)• Slit lamp biomicroscopy• Intraocular pressure (IOP) measurement• Dilated ophthalmoscopy
Efficacy Endpoints	
Primary Efficacy Endpoints:
 
Comparison of mean [REDACTED] Severity Assessment Score between the KPI-121 0.25% ophthalmic suspension group and the vehicle group:
 
• Visit 4 (based on the mean score for the 3 days prior to Visit 4) 
Comparison of mean posterior lid margin hyperemia [REDACTED] [REDACTED] at Visit 2 between the KPI-121 0.25% ophthalmic suspension group and the vehicle group:
 
• Visit 4 
Secondary Efficacy Endpoints:
 
Comparison of mean [REDACTED] Severity Assessment Score between the KPI-121 0.25% ophthalmic suspension group and the vehicle group:
 
• Visit 6 (based on the mean score for the 3 days prior to Visit 6) 
Comparison of mean posterior lid margin hyperemia [REDACTED] [REDACTED] at Visit 2 between the KPI-121 0.25% ophthalmic suspension group and the vehicle group:
 
• Visit 6

Exploratory Endpoints:

Comparison of mean investigator-rated assessment of conjunctival hyperemia between the KPI-121 0.25% ophthalmic suspension group and the vehicle group:

- Visit 4
- Visit 6

Comparison of mean investigator-rated character of the meibomian glands' contents between the KPI-121 0.25% ophthalmic suspension group and the vehicle group:

- Visit 4
- Visit 6

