3. TRIAL DESIGN

3.1. PRIMARY EFFICACY ENDPOINTS

Comparison of mean [REDACTED] Severity Assessment Score between the KPI-121 0.25% ophthalmic suspension group and the vehicle group:

- Visit 4 (based on the mean score for the 3 days prior to Visit 4)

Comparison of mean posterior lid margin hyperemia [REDACTED]

[REDACTED] at Visit 2 between the KPI-121 0.25% ophthalmic suspension group and the vehicle group:

- Visit 4

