3.2. SECONDARY EFFICACY ENDPOINTS

Comparison of mean [REDACTED] Severity Assessment Score between the KPI-121 0.25% ophthalmic suspension group and the vehicle group:

- Visit 6 [REDACTED]

Comparison of mean posterior lid margin hyperemia [REDACTED]

[REDACTED] at Visit 2 between the KPI-121 0.25% ophthalmic suspension group and the vehicle group:

- Visit 6

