9.1.2. Analysis of Efficacy

The primary analysis population will be the Intent-to-Treat (ITT) population, defined as all subjects randomized, for all analyses [REDACTED]

[REDACTED] A subset of efficacy analyses will be examined for the Efficacy Evaluable (EE) population, the definition of which will be outlined in the Statistical Analysis Plan and finalized prior to unmasking of study data pursuant to clinical data review.

The primary analysis of all ophthalmic efficacy measures will be based on the single study eye for each subject.

[REDACTED] Severity
Assessment Score between the KPI-121 0.25% ophthalmic suspension group and the vehicle group at Visit 4 (based on the mean score for the 3 days prior to Visit 2 and Visit 4); and (2) comparison of mean posterior lid margin hyperemia [REDACTED]

[REDACTED] at Visit 2 between the KPI-121 0.25% ophthalmic suspension group and the vehicle group at Visit 4.

Secondary and exploratory efficacy endpoints will be evaluated as elaborated in [Section 3](#).

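### Section 9.4 limits multiple imputation to the Visit 4 co-primary endpoints, and the visible text gives no missing-data method for the same two measures at Visit 6

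*Combined protocol and SAP*

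**What the plan says.** - **Method.** Section 9.4: "Multiple imputations will be employed to analyze incomplete data sets under the assumption that missing data are, at worst, characterized as missing at random (MAR").
- **Scope.** The same section closes: "Imputation will be carried out only on the co-primary endpoints and time points".
- **Co-primary time point.** Section 3.1 places both co-primary endpoints at Visit 4 (Day 15). The symptom score is taken at "Visit 4 (based on the mean score for the 3 days prior to Visit 4"), and posterior lid margin hyperemia is compared at the same visit.
- **Secondary endpoints.** Section 3.2 lists the same two measures at Visit 6 (Day 29). The Synopsis gives the symptom window as "Visit 6 (based on the mean score for the 3 days prior to Visit 6").
- **Population.** Section 9.1.2: "The primary analysis population will be the Intent-to-Treat (ITT) population, defined as all subjects randomized, for all analyses". The text that follows is blacked out.
- **Secondary analysis.** Section 9.1.2 says only: "Secondary and exploratory efficacy endpoints will be evaluated as elaborated in" Section 3, which lists comparisons of means and no missing-data method.
- **Inferential status.** Section 9.3: "All other reported *p*-values will be considered descriptive and hypothesis generating".
- **Follow-up.** Withdrawn subjects are not replaced (Section 5.3).

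**The concern.** The scope sentence is a stated rule rather than an omission. It covers the two measures at Day 15 and leaves them out at Day 29, where losses have had longer to accumulate. A plain comparison of available Visit 6 means needs more than MAR: either missingness must be unrelated to the scores, or its effect must be the same in both arms. The plan collects the Visit 2 and Visit 4 scores that could correct for score-related loss, then bars their use through imputation at Visit 6.

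At stake is the Visit 6 treatment estimate for the two main measures at the end of dosing. It could rest on a smaller and selected set of subjects than the Visit 4 estimate, under a stronger missing-data assumption, which would make the two visits hard to compare.

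**Working it through.** **Inputs from the documents.** 71 per group for 90% power with a 2-sided two-group t-test (Section 9.2, effect size and alpha blacked out); 5% significance level (Section 9.3); about 200 randomised at about 1:1, hence about 100 per arm (Synopsis). No dropout rate is given, so every loss figure below is an assumption.

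**1. The plan's own figure.** With the effect size and alpha blacked out, 71 cannot be reproduced. Back-solving at 2-sided alpha 0.05 gives a standardised effect of 0.548. An effect of 0.55 needs n = 70.4, rounded up to 71, with power 90.2% at 71. This shows consistency only. I take 0.55 SD as the working effect.

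**2. Is power the problem?** Subjects with Visit 6 data per arm = 100 × (1 − loss).

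| Loss per arm | n per arm | Power at 0.55 SD |
|---|---|---|
| 0% | 100 | 97.2% |
| 5% | 95 | 96.5% |
| 10% | 90 | 95.6% |
| 15% | 85 | 94.6% |
| 20% | 80 | 93.3% |
| 29% | 71 | 90.2% |

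Power is not the issue. Bias is.

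**3. Bias by arithmetic.** Suppose subjects without Visit 6 data would have scored g SD worse than those with it, in both arms. In each arm the full mean is the available mean plus loss × g. The difference between arms is therefore off by

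g × (vehicle loss − active loss).

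With 15% against 5% loss the bracket is 0.10:

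- g = 0.25: 0.025 SD
- g = 0.50: 0.05 SD
- g = 1.00: 0.10 SD

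With equal loss and equal g the error is 0. If the active arm loses more, the sign reverses and the error favours the drug.

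**4. Bias when loss depends on the Visit 4 score (MAR).** Simulation with 1,000,000 subjects per arm, a true effect of 0.55 SD at both visits, Visit 4 to Visit 6 correlation 0.6–0.8, and logistic dropout on the Visit 4 score with slope 1–1.5 and the same rule in both arms.

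- At about 13–23% vehicle and 9–14% active loss, the available-data Visit 6 effect is 4.4–13.9% too small. That is 0.044 × 0.55 = 0.024 SD to 0.139 × 0.55 = 0.076 SD.
- At 5–10% vehicle loss it is 0.01–0.04 SD too small.
- Predicting missing Visit 6 scores from Visit 4 by regression on such data returns 0.548–0.553, so imputation removes the bias under MAR.

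**5. Scale.** With 90 per arm the standard error of a Visit 6 difference is √(2/90) = 0.149 SD. A bias of 0.024–0.076 SD is 0.024/0.149 = 0.16 to 0.076/0.149 = 0.51 of a standard error.

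**6. How much loss is plausible?** The rules pull in two directions.

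- Against loss: rescued subjects stay through Visit 6 (Sections 5.2 and 8.4), and subjects who stop early should have Visit 6 assessments attempted (Sections 5.1.8 and 5.3).
- Towards loss: where the full set is not feasible, the minimum set in Section 5.1.8 omits the investigator-rated signs, and so lid margin hyperemia. Section 5.1.7 has discontinuing subjects' data entered on Visit 6 forms, but the visible text does not say whether early values count as Visit 6 values.

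**The case against.** The strongest reply is that limiting imputation to the confirmatory endpoints is a deliberate and defensible choice in a Phase 2 trial. Visit 6 p-values are descriptive, and Section 9.4 already asks for the reasons for missing data and any imbalance between arms to be evaluated. That stands as a limit on the consequence. It does not remove bias from the estimate.

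Four stronger readings are tempting, and the documents do not support them.

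- **That the plan prescribes an observed-case analysis at Visit 6.** It never uses the term. Part of Section 9.1.2 is blacked out, and the Statistical Analysis Plan it cites is not in the text reviewed. A likelihood-based repeated-measures model there would impute nothing yet still use Visit 4 data from subjects without Visit 6. The supportable statement is that no method is visible.
- **That Visit 6 breaches a promise to analyse everyone randomised.** The population sentence runs into blacked-out text, and the hyperemia endpoint carries a blacked-out qualifier tied to Visit 2. Its exploratory change-from-baseline counterpart is limited to subjects with grade 1 or more in at least one lid margin at Visit 2. A similar limit on the secondary endpoint cannot be ruled out.
- **That poor responders will disappear.** The rescue and early-termination rules aim to keep them in view, so score-related loss is possible but not shown to be likely.
- **That the bias is large or could create an effect from nothing.** If vehicle losses were selective and active losses random, 5%, 10% or 15% loss per arm would give 0.046, 0.085 or 0.123 SD with no true effect. That needs opposite loss mechanisms in the two arms, and nothing in the documents points to that.

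**Conclusion.** The point holds in a limited form. Section 9.4 expressly leaves the Visit 6 secondary endpoints out of the planned imputation, and the visible text puts nothing in its place. As written, their means would in effect be compared among subjects with Visit 6 data. That comparison is biased under the plan's own MAR assumption if loss after Visit 4 depends on earlier scores and differs between arms.

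The size is modest: roughly 0.01–0.08 SD for assumed vehicle-arm losses of about 5–25%, a working effect of 0.55 SD and a correlation of 0.6–0.8 between visits. It reaches 0.10 SD only with a full-SD gap and 15% against 5% loss. It is about zero when loss is alike in both arms, and the direction depends on who leaves. These figures rest on assumptions, because no dropout rate is given. The co-primary conclusion and type I error are not affected. The change is worth making because it is specific and cheap, not because the trial's main result is at risk.

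**What to change.** Replace the last sentence of Section 9.4 with:

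> Multiple imputation under MAR will be applied to the co-primary endpoints at Visit 4 and to the secondary endpoints at Visit 6, in the analysis population defined for each endpoint. The Visit 6 imputation will be run separately and will use treatment arm, stratification factors and the Visit 2 and Visit 4 scores, so that the primary Visit 4 imputation is unchanged. Observed-case Visit 6 results and the number contributing per arm will be reported as supportive.

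Two features are deliberate. The separate run matters because adding Visit 6 to a single model would also alter the imputed primary values. Referring to the population defined for each endpoint avoids a clash with the blacked-out Visit 2 qualifier on hyperemia. Exploratory endpoints can stay as planned. If the separate Statistical Analysis Plan already specifies a repeated-measures model for Visit 6, Section 9.4 needs only to say so.

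The cost is a little more analysis work and reliance on MAR at a second visit. Sample size, alpha and study conduct do not change.

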9.5. PROCEDURE FOR REPORTING DEVIATIONS FROM THE STATISTICAL PLAN

Any deviations from the statistical analysis plan will be described and a justification given in the final clinical study report.

10. DIRECT ACCESS TO SOURCE DATA/DOCUMENTS

The Investigator will permit trial-related monitoring, audits, IRB review, and regulatory inspection(s) by providing direct access to source data and documents (such as tests performed as a requirement for participation in the study and other medical records required to confirm information contained in the case report form such as medical history) to the monitor.

11. QUALITY CONTROL

The progress of the study will be monitored by on-site, written, e-mail, and telephone communications between personnel at the study center and the sponsor (or designated monitor). The Investigator will allow Kala Pharmaceuticals, Inc. monitors or designee to inspect all CRFs; subject records (source documents); signed informed consent forms; HIPAA authorizations; records of investigational product receipt, storage, and disposition; and regulatory files related to the study.

12. ETHICS

12.1. Institutional Review Board

This protocol and the informed consent form must be approved by an appropriately constituted and qualified IRB and the approvals made available to the sponsor or designee prior to the start of enrollment into the study. Materials used to recruit subjects will be approved by the appropriate IRB and the approvals made available to the sponsor or designee prior to their use. In addition, the Investigator's Brochure should be submitted to the IRB. Written IRB approval must adequately identify the protocol and informed consent form. Copies of all approved materials, all correspondence with the IRB, and written approval from the IRB must be made available to the sponsor (or designated monitor).

Any modification of study procedures or amendments to the protocol must be approved by the IRB prior to implementation. In the event that a modification or amendment is considered by the Investigator to be immediately necessary to ensure subject safety, the Investigator will promptly notify his or her IRB and the sponsor.

Investigators will report all SAEs reported at their site to their IRB, as appropriate.

12.2. Informed Consent Requirements

Written informed consent will be obtained from each participant prior to any study-related procedures being performed (prior to or upon Visit 1- Screening). A copy of the signed and dated informed consent document will be given to each subject. The original signed and dated informed consent document must be maintained in the study files at the investigative site and be available for sponsor or designee review.

Each informed consent will contain Investigator contact information with a telephone number the subject or the subject's authorized representative can call 24 hours a day if they have medical concerns.

13. DATA HANDLING AND RECORDKEEPING

All procedures for the handling and analysis of data will be conducted using GCP and will meet ICH guidelines and US FDA regulations for the handling and analysis of data for clinical trials.

13.1. Data Quality Control and Reporting

After data have been entered into the study database, a system of computerized data validation checks will be implemented and applied to the database. Query reports pertaining to data omissions and discrepancies will be forwarded to the clinical Investigator and monitor(s) for resolution. The study database will be updated in accordance with the resolved query reports. All changes to the study database will be documented.

13.2. Records Retention

The study center will retain all records related to the study in accordance with local and ICH GCP guidelines.

14. PUBLICATION POLICY

The institution and Investigators participating in this trial shall have no right to publish or present the results of this study without the prior written consent of the sponsor.

16. APPENDICES

CONFIDENTIAL

APPENDIX 1: SUMMARY OF EVENTS

Procedures	Visit 1	Visit 2	Visit 3	Visit 4	Visit 5	Visit 6
	Screening	Randomization	█	Study Visit	█	End of Study Visit
	14 ± 1 Days Prior to Day 1	Day 1	Day 8 (±1 day)	Day 15 (±1 day)	Day 22 (±1 day)	Day 29 (±1 day)
Informed Consent, HIPAA Authorization and Medical History	X					
Concomitant Medication Query	X	X	X	X	X	X
Inclusion/Exclusion	X	X				
█ Assessment	X					
UPT ^a	X					X
AE Assessment	X	X	X	X	X	X
Subject-Rated Ocular Discomfort Assessment	X	X	X	X	X	X
Investigator-Rated Assessment of Signs of MGD	X	X		X		X
Investigator-Rated Assessment of Bulbar Conjunctival Hyperemia	X	X		X		X
█	█	█	█	█	█	
TFBUT	X	X		X		X
Corneal Fluorescein Staining	X	X		X		X
Unanesthetized Schirmer Test	X					
BCVA	X	X		X		X
Slit Lamp Biomicroscopy	X	X		X		X
IOP Measurement	X	X		X		X
Dilated Ophthalmoscopy	X					X
Investigational Product Administration in Clinic	X	X				
Dispense Investigational Product	X ^b	X		X		
Collect Investigational Product		X ^b		X		X

Procedures	Visit 1	Visit 2	Visit 3	Visit 4	Visit 5	Visit 6
	Screening	Randomization		Study Visit		End of Study Visit
	14 ± 1 Days Prior to Day 1	Day 1	Day 8 (±1 day)	Day 15 (±1 day)	Day 22 (±1 day)	Day 29 (±1 day)
	X	X	X	X	X	
		X	X	X	X	X

^aWomen of childbearing potential only. ^bRun-In Drug

APPENDIX 2: SUBJECT-RATED OCULAR DISCOMFORT ASSESSMENT

Subjects will be asked to subjectively rate their ocular discomfort severity and frequency at Visits 1-6. Site personnel will ask the subject the following question and record their answer in the eCRF.

Severity of Symptoms

On average over the past day, how would you rate the severity of your ocular discomfort (such as irritation, dryness, burning, fluctuating vision at near tasks)?

- 0 = None
- 1 = Mild
- 2 = Moderate
- 3 = Severe
- 4 = Very Severe

Frequency of Symptoms

On average over the past day, how often have you had this level of ocular discomfort (such as irritation, dryness, burning, fluctuating vision at near tasks)?

- 0 = Never
- 1 = Sometimes
- 2 = Often
- 3 = Constantly

APPENDIX 3: [REDACTED]

Subjects will be asked to subjectively rate their ocular discomfort severity and frequency at Visit 1 for eligibility. [REDACTED]

The length of the line between the [REDACTED] starting point and the first point where the subject's mark crosses the line will be measured and recorded in millimeters.

[REDACTED] **SEVERITY ASSESSMENT**

Please place a single line across the line below to indicate how severe, [REDACTED] you feel your eye discomfort (for example, irritation, dryness, burning, or fluctuating vision during reading or computer use) was:

[REDACTED] _____ [REDACTED]

[REDACTED] **FREQUENCY ASSESSMENT**

Please place a single line across the line below to indicate how often, [REDACTED] you feel your eye discomfort (for example, irritation, dryness, burning, or fluctuating vision during reading or computer use) was:

[REDACTED] _____ [REDACTED]

APPENDIX 4: INVESTIGATOR-RATED ASSESSMENT OF SIGNS OF MGD

Eyelid Margin Hyperemia (lower eyelid):

0 = Normal	Normal age-appropriate redness and vasculation.
1 = Mild	Slightly dilated blood vessels; vessels colored pink, present in greater than 25% of the lower eyelid margin
2 = Moderate	More apparent dilation of blood vessels; vessels red, present in greater than 25% of the lower eyelid margin.
3 = Severe	Increased vascularity of the eyelid margin; numerous and obvious dilated blood vessels, deep red in color, present in greater than 25% of the lower eyelid margin.
4 = Very Severe	Clearly increased vascularity of the eyelid margin; numerous dilated blood vessels deep red color, present in greater than 75% of the lower eyelid margin.

Character of Meibomian Gland Content (10 glands in the middle part of lower lid)

[figure not shown]
0 = Normal	Clear liquid
1 = Mild	Hazy, turbid liquid
2 = Moderate	Turbid liquid with clumps
3 = Severe	Solid (paste)
4 = No glands expressible	

The most severe finding in any one meibomian gland should be recorded for this evaluation

Expressibility of Meibomian Gland (10 glands in the middle part of lower lid)

0 = Normal	9 – 10 glands expressible
1 = Mild	6 – 8 glands expressible
2 = Moderate	3 – 5 glands expressible
3 = Severe	1 – 2 glands expressible
4 = No glands expressible	

APPENDIX 5: INVESTIGATOR-RATED ASSESSMENT OF BULBAR CONJUNCTIVAL HYPEREMIA
Investigators will rate bulbar conjunctival hyperemia at Visits 1, 2, 4, and 6 using the Cornea and Contact Lens Research Unit (CCLRU).

- 0 = None
- 1 = Very Slight
- 2 = Slight
- 3 = Moderate
- 4 = Severe

Appendix 6: Unanesthetized Schirmer Test

Unanesthetized Schirmer Test will be conducted at Visit 1.
Identical Schirmer Test strips will be supplied to each site.

Unanesthetized Schirmer Test

- While still in the plastic sheath, fold the notched end of the unanesthetized Schirmer Test at the apex of “v”. Additionally, fold a partial second fold at the halfway point of the strip so that the strip does not lie directly in the subject’s line of sight.
- Remove the right eye strip from the sheath.
- Ask the subject to look up and gently draw the right lower lid in a downward and temporal direction.
- Place the rounded end of the strip toward the temporal one-third of the lower eyelid.
- Repeat this procedure in the left eye.
- Darken the room, but ensure that the Large E of the ETDRS chart is visible.
- Instruct the subject to relax and look at the chart while blinking normally or have patients gently close eyes.
- Remove strips after 5 minutes.
- After removing the strips, with a sharp pencil draw a horizontal line across the leading edge of moisture and a second horizontal line across the lowest point of moisture.
- Using a ruler and/or the millimeters recorded on the strips, measure a point halfway between the 2 lines and record this as the amount of wetting.

